8.2 Algorithm for the Overall Efficacy Assessment for Surgical Prophylaxis

The evaluation of overall efficacy of the treatment in surgeries based on the intraoperative and postoperative assessment is defined as described below:

| Intraoperative assessment | Postoperative assessment | | | |
|---------------------------|--------------------------|----------|----------|----------|
| | Excellent | Good | Moderate | None |
| Excellent | Excellent | Good | Good | Moderate |
| Good | Good | Good | Moderate | Moderate |
| Moderate | Good | Moderate | Moderate | None |
| None | Good | Moderate | None | None |

STATISTICAL ANALYSIS PLAN**Protocol No: WIL-30**

Version Number: 1.2

Date of Issue: 2019-07-08

Page 27 of 27

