7.2.4 Efficacy of the Treatment of Breakthrough BEs

At the end of a BE, treatment efficacy will be assessed by the patient (together with the Investigator in case of on-site treatment) using the predefined criteria detailed in **Table 2**.

Table 2 Efficacy Assessment of the Treatment of Breakthrough BEs

Excellent	Abrupt pain relief and/or unequivocal improvement in objective signs of bleeding within approximately 8 hours after a single injection		
Good	Definite pain relief and/or improvement in signs of bleeding within approximately 8–12 hours after an injection, requiring up to 2 injections for complete resolution		
Moderate	Probable or slight beneficial effect within approximately 12 hours after the first injection, requiring more than 2 injections for complete resolution		
None	No improvement within 12 hours, or worsening of symptoms, requiring more than 2 injections for complete resolution		

The **proportion of BEs successfully treated with IMP** will be evaluated for all BEs taken together and by BE severity. All efficacy ratings assessed as either 'excellent' or 'good' will be considered 'successfully treated.'

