7.2.6.1 At the End of Surgery (by Surgeon)

At the end of surgery, the hemostatic efficacy of Wilate will be assessed by the surgeon using the criteria listed in Table 3.

 Table 3
 Efficacy Assessment at the End of Surgery

Excellent	Intraoperative blood loss was lower than or equal to the average expected blood loss for the type of procedure performed in a patient with normal hemostasis and of the same sex, age, and stature.
Good	Intraoperative blood loss was higher than the average expected blood loss but lower or equal to the maximal expected blood loss for the type of procedure in a patient with normal hemostasis.
Moderate	Intraoperative blood loss was higher than the maximum expected blood loss for the type of procedure performed in a patient with normal hemostasis, but hemostasis was controlled.
None	Hemostasis was uncontrolled, necessitating a change in the clotting factor replacement regimen.

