7.2.6.3 Overall Efficacy Assessment at the End of the Postoperative Period (by Investigator)

Overall efficacy using the 'excellent,' 'good,' moderate,' and 'none' scale taking both the intraand postoperative assessments into account will be assessed by the Investigator.

Table 5 Algorithm for the Overall Efficacy Assessment for Surgical Prophylaxis

Intraoperative assessment	Postoperative assessment				
	Excellent	Good	Moderate	None	
Excellent	Excellent	Good	Good	Moderate	
Good	Good	Good	Moderate	Moderate	
Moderate	Good	Moderate	Moderate	None	
None	Moderate	Moderate	None	None	

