5.9 Surgeries

Efficacy in surgical prophylaxis will be analyzed descriptively, presenting summary tables and listing on all aspects of surgical treatment and procedures as well as efficacy ratings.

| | |
|---|---------------|
| 
STATISTICAL ANALYSIS PLAN Protocol No: WIL-30
 | |
| Version Number: 1.2 | Page 21 of 27 |
| Date of Issue: 2019-07-08 | |

The following surgery-related parameters will be presented:

- Number of minor and major surgeries
- Location, severity (minor or major, for definitions see protocol), and type (planned or emergency) of surgery
- Expected and actual duration of surgical procedure
- Expected and actual blood loss
- Pre-, intra-, and/or postoperative IMP administration data (only listed)
- Pre-, intra-, and postoperative FVIII plasma levels (only listed)
- VWF:Ag and VWF:Ac (descriptive statistics including changes to pre-infusion)
- Frequency and amount of blood transfusion requirements
- Presence of wound hematomas and whether or not they require surgical evacuation (only listed)
- Assessment of efficacy of surgical prophylaxis:
 1. at the end of surgery by the surgeon
 2. at end of the postoperative period by the hematologist
 3. Overall efficacy taking both the intra- and postoperative assessments into account assessed by the Investigator.
- Number of successively treated surgeries ('excellent' or 'good' overall efficacy rating)
- Concomitantly administered products (only listed)
- Narrative describing the outcome and efficacy of the intervention (only listed)
- Inhibitor testing (within 3–8 weeks after the end of the surgery, this visit may coincide with another study visit with scheduled inhibitor testing)

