| C _{max} | Maximal measured concentration after end of IMP infusion (peak concentration) |
| ED | Exposure day = each calendar day the subject received IMP |
| Incremental recovery (IVR) | $IVR = \frac{(C_{max} - C_0) \cdot BW}{D}$ where BW stands for the body weight in kg and D is the dose according to the actual potency of the FVIII concentrate as described in above |
| Labelled potency | Potency of IMP (IU) based on label of vial (IU). Dosing analyses will be based on labelled potency |
| MRT | Mean residence time $MRT = \frac{AUMC}{AUC}$ |
| Success (for bleeding episodes and surgeries) | Excellent or good efficacy rating |

| | |
|----------------------------------|---------------|
| STATISTICAL ANALYSIS PLAN | |
| Protocol No: WIL-30 | |
| Version Number: 1.2 | Page 26 of 27 |
| Date of Issue: 2019-07-08 | |

| Variable | Description |
|-----------|--|
| $T_{1/2}$ | In vivo half-life using linear regression on the terminal phase of the logarithm of the concentration; $T_{1/2} = \frac{\ln(2)}{K}$ (where K , the elimination rate constant, is determined as the slope of the regression line) |
| T_{max} | Time to reach maximum plasma concentration (Timing starts at end of infusion) |
| Vd | Volume of distribution $Vd = CL \cdot MRT$ |

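### SAP 8.2 rates an intraoperative None with a postoperative Excellent as Good overall, where Protocol v02 Table 5 says Moderate, so a surgery with uncontrolled haemostasis could count as a success

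*SAP*

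**What the plan says.** Protocol 7.2.6 has each surgery rated twice. The surgeon rates haemostasis at the end of surgery (Table 3), and the haematologist rates it at the end of the postoperative period (Table 4). The Investigator then gives an overall rating, for which Table 5 is headed as the algorithm. On the surgeon's scale, None means: "Hemostasis was uncontrolled, necessitating a change in the clotting factor replacement regimen".

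For an intraoperative None, with the postoperative rating running Excellent, Good, Moderate, None, the overall ratings are:

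- Protocol v02, Table 5: "None Moderate Moderate None None"
- SAP v1.2, section 8.2: "None | Good | Moderate | None | None"

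(The first word of each row is the intraoperative rating.) SAP v1.0 and v1.1 carry the same row as v1.2.

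The SAP introduces its table with "The evaluation of overall efficacy of the treatment in surgeries based on the intraoperative and postoperative assessment is defined as described below". SAP 5.9, however, lists the item to be presented as "Overall efficacy taking both the intra- and postoperative assessments into account assessed by the Investigator", and then asks for "Number of successively treated surgeries ('excellent' or 'good' overall efficacy rating"), presumably meaning successfully treated. SAP 8.1 defines success, for bleeding episodes and surgeries alike, as "Excellent or good efficacy rating". The protocol sets a success threshold for bleeding episodes only, in 7.2.4: "All efficacy ratings assessed as either 'excellent' or 'good' will be considered 'successfully treated".

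SAP 3.2 states that the analysis departs from the protocol nowhere. The title page of SAP v1.2 names protocol Version 02 (Ukraine only) and Version 03 as the versions it serves.

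**The concern.** The SAP table is presented as the protocol's algorithm but is more lenient in one cell. A surgery that the surgeon rated None, the worst category, becomes Good overall if the postoperative course is rated Excellent. Because the SAP counts Good as success, the surgery moves from the failures to the successes. The difference favours the product, and nothing in the SAP acknowledges or explains it.

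The two ratings cover different periods and come from different raters, and nothing in Tables 3 and 4 rules out None followed by Excellent. At stake is whether the reported number of successfully treated surgeries follows the protocol's own rule, in a study meant to support a US hemophilia A indication (Protocol 1.2 and 1.3).

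**Working it through.** No sample size, power or error rate is involved, so the check is a comparison of the two tables followed by a count.

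**Inputs.** Protocol v02 Table 5 (7.2.6.3), the SAP v1.2 table (8.2), and the success rule in SAP 5.9 and 8.1 (Excellent or Good).

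**Step 1: the tables side by side.** Each cell shows protocol / SAP.

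| Intraoperative | Postop. Excellent | Postop. Good | Postop. Moderate | Postop. None |
|---|---|---|---|---|
| Excellent | Excellent / Excellent | Good / Good | Good / Good | Moderate / Moderate |
| Good | Good / Good | Good / Good | Moderate / Moderate | Moderate / Moderate |
| Moderate | Good / Good | Moderate / Moderate | Moderate / Moderate | None / None |
| None | **Moderate / Good** | Moderate / Moderate | None / None | None / None |

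Fifteen of 16 cells agree. The exception is intraoperative None with postoperative Excellent.

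**Step 2: apply the SAP success rule.** Cells rated Good or better, by row from Excellent to None:

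- Protocol: 3 + 2 + 1 + 0 = 6 of 16
- SAP: 3 + 2 + 1 + 1 = 7 of 16

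In the intraoperative None row, 0 of 4 cells are successes under the protocol and 1 of 4 under the SAP. Under Table 5, no surgery with uncontrolled intraoperative haemostasis can be a success. Under SAP 8.2, one combination can.

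**Step 3: which cell looks out of place?** The protocol table is symmetric: exchanging the intraoperative and postoperative ratings never changes the overall rating. In particular, Excellent then None and None then Excellent both give Moderate. In the SAP, Excellent then None gives Moderate but None then Excellent gives Good, and this is the only asymmetric pair. The SAP also gives intraoperative Moderate and intraoperative None the same overall rating when the postoperative rating is Excellent. No reason is given for either feature. This suggests an error in the SAP but does not prove one.

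**Step 4: is it a declared change?** SAP 3.2 declares no departure. The v1.2 change-control entry mentions a bleeding subgroup and added derivation formulas, and says nothing about this table. The row is already in SAP v1.0 of 2017-04-26, so it predates protocol Version 03 (2018-07-06).

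**Step 5: effect on the count.** Let *k* be the number of surgeries with the pair None, Excellent. If the overall rating is derived from SAP 8.2, the success count is too high by *k* relative to Table 5. If the Investigator's recorded rating is used, the SAP table does not enter the count. The documents give no expected number of surgeries, so no percentage can be stated.

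**The case against.** The strongest reply is that the cell will probably never matter. Surgical efficacy is exploratory and descriptive, only 10 children are planned, and surgery is incidental to the study. A surgery would have to occur, be rated None by the surgeon and Excellent by the haematologist, and have its overall rating computed from 8.2. SAP 5.9 and the SAP's surgical flow chart both attribute the overall rating to the Investigator, who would work from the protocol's table. The surgeon's and haematologist's ratings are also presented separately, with listings and a narrative for each intervention, so such a case would be visible. Finally, the supplied protocol is Version 02, for Ukraine only. Version 03 is not available here, nor is the Version 1.0 that SAP section 1 still lists as its source, so one cannot be sure which table agrees with those versions.

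Much of this stands as a limit on size. It does not remove the contradiction. SAP 8.2 says the overall evaluation is defined by its table, so a programmer could reasonably derive the rating from it, and 5.9 does not say otherwise. If the recorded rating is analysed instead, the SAP still carries a rule that conflicts with the one the Investigator was given. Agreement with Version 03 would not settle the matter either, because the SAP title page also names Version 02. Visibility in listings would help a careful reader, but the headline count would still be wrong against Table 5.

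**Conclusion.** The discrepancy is real. One of 16 cells differs between SAP 8.2 and Protocol v02 Table 5, it lies across the SAP's success threshold, and it runs in the product's favour without being declared. The consequence is one extra success for each surgery rated None then Excellent, and zero if no such surgery occurs or if the Investigator's recorded rating is counted.

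The conclusion rests on Protocol v02 being a governing version, as the SAP title page says. It assumes nothing about the content of Version 03. The success threshold for surgeries comes from the SAP alone. No primary or secondary result is affected. It should be fixed because the contradiction is certain and the correction costs almost nothing, although its practical weight is small.

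**What to change.** 1. Check the same cell in protocol Version 03. Then set SAP 8.2, intraoperative None with postoperative Excellent, to Moderate so that it matches Table 5. If Good is intended, declare the difference in SAP 3.2 with a reason.
2. In SAP 5.9, state whether the overall rating analysed is the one recorded by the Investigator or the one derived from 8.2, and that surgical success is counted from a rating consistent with Protocol Table 5.

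The cost is one table cell and one sentence, with no new data. The success count changes only if this pair of ratings occurs and the overall rating is derived from 8.2. It then falls by one per such surgery.

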8.3 List of Tables, Listings, Figures

A complete lists of tables, listings figures (TLFs) will be given in a separate document which can be updated without updating the SAP. The list will serve as a reference for both the Sponsor, the trial statistician and the statistical programmer and includes the totality of statistical output to be produced. Therefore, this list will be approved by both parties before commencing the statistical programming.

All output will be headed with an appropriate heading specifying the study ID and abbreviated study title.

All output will be dated and have page numbers in the form 'Page [x / y]' where x denotes the current page within an output and y the total number of pages of that output.

All statistical output will identify the underlying analysis populations and indicate the number of subjects / events in this population (N) and the number of subject/events actually contributing to the particular output (n). All statistical output will be presented per treatment group and in total (if applicable).

All subject listings will contain additionally to the subject identification the analysis population and the treatment group.
